10.8. Appendix 8: Provisions for Changes in Study Conduct During Exceptional Circumstances

Implementation of this appendix

The changes to procedures described in this appendix are temporary measures intended to be used only during specific time periods as directed by the sponsor in partnership with the investigator.

Exceptional circumstances

Exceptional circumstances are rare events that may cause disruptions to the conduct of the study. Examples include pandemics or natural disasters. These disruptions may limit the ability of the investigators, participants, or both to attend on-site visits or to conduct planned study procedures.

Implementing changes under exceptional circumstances

In an exceptional circumstance, after receiving the sponsor's written approval, sites may implement changes if permitted by local regulations.

After approval by local Ethical Review Boards, regulatory bodies and any other relevant local authorities, implementation of these exceptional circumstance changes will not typically require additional notification to these groups, unless they have specific requirements in which notification is required (for example, upon implementation and suspension of changes). All approvals and notifications must be retained in the study records.

If the sponsor grants written approval for changes in study conduct, the sponsor will also provide additional written guidance, if needed.

Considerations for making a change

The prevailing consideration for making a change is ensuring the safety of study participants. Additional important considerations for making a change are compliance with Good Clinical Practice, enabling participants to continue safely in the study and maintaining the integrity of the study.

Informed consent

Additional consent from the participant will be obtained, if required, for:

- participation in remote visits, as defined in Section “Remote Visits,”
- a change in the method of study intervention administration,
- dispensation of additional study intervention during an extended treatment period,
- alternate delivery of study intervention and ancillary supplies, and
- provision of their personal or medical information required prior to implementation of these activities.

Changes in study conduct during exceptional circumstances

Changes in study conduct not described in this appendix, or not consistent with applicable local regulations, are not allowed.

The following changes in study conduct will not be considered protocol deviations.

Remote visits***Types of remote visits***

Telemedicine: Telephone or technology-assisted virtual visits, or both, are acceptable to complete appropriate assessments. Assessments to be completed in this manner include, but are not limited to, medical history, AEs and product complaints, concomitant medications, diabetes education, reminding 7-point SMBG, reviewing diary.

Other alternative locations: Laboratory testing in local hospital is permitted based on the discretion of investigator with the approval of sponsor.

Data capture

In source documents and the CRF, the study site should capture the visit method, with a specific explanation for any data missing because of missed in-person site visits.

Safety reporting

Regardless of the type of remote visits implemented, the protocol requirements regarding the reporting of AEs, SAEs, and product complaints remain unchanged.

Return to on-site visits

Every effort should be made to enable participants to return to on-site visits as soon as reasonably possible, while ensuring the safety of both the participants and the site staff.

Local laboratory testing option

Local laboratory testing may be conducted in lieu of central laboratory testing. However, central laboratory testing must be retained for: HbA1c and FSG at Visit 3 and Visit 11. The local laboratory must be qualified in accordance with applicable local regulations. Clinically significant laboratory findings could be recorded as an AE in the AE CRF at the discretion of investigator.

Study intervention and ancillary supplies (including participant diaries)

When a participant is unable to go to the site to receive study supplies during normal on-site visits, the site should work with the sponsor to determine appropriate actions. These actions may include:

- asking the participant to go to the site and receive study supplies from site staff without completion of a full study visit,
- asking the participant's designee to go to the site and receive study supplies on a participant's behalf,
- arranging delivery of study supplies, and

These requirements must be met before action is taken:

- Alternate delivery of study intervention should be performed in a manner that does not compromise treatment blinding and ensures product integrity. The existing protocol requirements for product accountability remain unchanged, including verification of participant's receipt of study supplies.

- When delivering supplies to a location other than the study site (for example, participant's home), the investigator, sponsor, or both should ensure oversight of the shipping process to ensure accountability and product quality (that is, storage conditions maintained and intact packaging upon receipt).
- Instructions may be provided to the participant or designee on the final disposition of any unused or completed study supplies.

Screening period guidance

To ensure safety of study participants, laboratory values and other eligibility assessments taken at Visit 1 are valid for a maximum of 60 days. The following rules will be applied for active, nonrandomized participants whose participation in the study must be paused due to exceptional circumstances:

- If screening is paused for less than 60 days from Visit 1 to Visit 3: the participant will proceed to the next study visit per the usual SoA, provided that Visit 3 must be conducted within 60 days from Visit 1.
 - The site should conduct the next visit if the participant's eligibility criteria are confirmed, and the site should document the reason for delay.
 - Due to the pause in screening, sites should also reconfirm the impacted participant's consent and document this confirmation in the source documentation.
- If screening is paused for more than 60 days from Visit 1: The participant must be discontinued because of screening interruption due to an exceptional circumstance. This is documented as a screen failure in the CRF.

Adjustments to visit windows

Whenever possible and safe to do so, as determined by the investigator's discretion, participants should complete the usual SoA. To maximize the possibility that these visits can be conducted as on-site visits, the windows for visits may be adjusted, upon further guidance from the sponsor. This minimizes missing data and preserves the intended conduct of the study.

This table describes the allowed adjustments to visit windows.

| Visit Number | Tolerance |
|-------------------------|--|
| Visit 1 (Screening) | No change. |
| Visit 2 | At least 4 days before Visit 3. |
| Visit 3 (Randomization) | Within 60 days after Visit 1. |
| Visit 3 through 8 | Within 7 days before or after the intended date. |
| Visit 9 through 10 | Within 14 days before or after the intended date. |
| Visit 11 or Visit 99 | Within 14 days before the intended date, or up to 28 days after the intended date. |
| Visit 801 | No change. |

For participants whose visits have extended windows at Visit 11, additional study intervention may need to be provided to avoid interruption and maintain overall integrity of the study.

Documentation

Changes to study conduct will be documented

Sites will identify and document the details of how participants, visit types, and conducted activities were affected by exceptional circumstances. Dispensing/shipment records of study intervention and relevant communications, including delegation, should be filed with site study records.

Source documents at alternate locations

Source documents generated at a location other than the study site should be part of the investigator's source documentation and should be transferred to the site in a secure and timely manner.

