Visit 99 is only applicable to participants who discontinue the study treatment prematurely before Week 40 and decline to complete the remaining study visits but are willing to return for Visit 99 at Week 40 after randomization. This visit is critical to ensure complete data collection for the primary and key secondary endpoints.

Participants should attend this visit in the fasting state. Procedures to be completed are:

- measurement of HbA1c, FSG and weight
- listing of concomitant medications, and
- assessment of AEs.

For participants unwilling to attend this visit, their refusal to attend should be documented in the participant medical record.

Study Period III (safety follow-up period)

Safety follow-up (Visit 801) visits:

All participants who complete the treatment period (complete Visit 11 or Visit 99) are required to complete Visit 801, a safety follow-up visit approximately 4 weeks after their last treatment visit. Participants discontinuing the study early and performing an early termination (ET) visit

will also be asked to perform the safety follow-up visit, so that the safety follow-up visit will be their final visit. During the safety follow-up period, participants will not receive study intervention. Participants may be treated with another glucose-lowering intervention decided upon by the investigator (except for prohibited antihyperglycemic medications, see section 6.9.1). If any new antihyperglycemic medication is initiated during the safety follow-up period, it will not be classified as rescue therapy.

Participants are also required to return any remaining study diaries to the study site at the end of this period.

The participants who complete the treatment period (complete Visit 11 or Visit 99) and safety follow-up (Visit 801) are considered as complete the study.

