7.1. Discontinuation of Study Intervention

When necessary, a participant may be permanently discontinued from study intervention. If so, the participant will discontinue the study intervention, could receive another glucose-lowering intervention and will remain in the study and follow procedures for all remaining study visits, as shown in the SoA. The new glucose-lowering intervention will be recorded on the CRF specified for collecting antihyperglycemic medications.

A participant should be permanently discontinued from study intervention if

- the participant becomes pregnant during the study (will also be withdrawn from the study)
- the participant is diagnosed with T1DM (will also be withdrawn from the study)
- the participant discontinues due to a hepatic event or liver test abnormality (see section 7.1.1)
- the participant requests to discontinue study intervention.
- the participant is diagnosed with an acute or chronic pancreatitis
- the participant is diagnosed with MTC after randomization, or has post randomization calcitonin value ≥ 35 ng/L that has increased at least 50% over baseline
- the participant is diagnosed with an active or untreated malignancy (other than basal or squamous cell skin cancer, in situ carcinomas of the cervix, or in situ prostate cancer) after randomization
- the participant has any significant study intervention related hypersensitivity reaction
- the participant has any other TEAE, SAE, or clinically significant laboratory value for which the investigator believes that permanent study intervention discontinuation is the appropriate measure to be taken.

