8.1. Efficacy Assessments

Primary efficacy assessments

The primary efficacy measurement in this study is change in HbA1c values from baseline to Week 40, as determined by the central laboratory. Blood samples for HbA1c measurements will be collected at specific clinic visits as summarized in the SoA, Section 1.3.

Other efficacy assessments

Other efficacy assessments include change in HbA1c, FSG, body weight, 7-point SMBG, C-peptide, insulin level, waist circumference, BMI, lipids, urinary albumin to creatinine ratio, and patient-reported outcomes (PROs).

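### Appendix 8 protects central HbA1c and FSG at Visits 3 and 11 but omits Visit 99, so some Week 40 values could be local, and the SAP has no rule for them

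*Protocol*

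**What the plan says.** Protocol Section 10.8 (Appendix 8) sets out what may change during events such as pandemics or natural disasters. Its local laboratory option reads "Local laboratory testing may be conducted in lieu of central laboratory testing", limited by one sentence: "central laboratory testing must be retained for: HbA1c and FSG at Visit 3 and Visit 11". The list of permitted changes opens with "The following changes in study conduct will not be considered protocol deviations".

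Protocol Section 8.1 defines the primary measurement as "change in HbA1c values from baseline to Week 40, as determined by the central laboratory". The objectives table in Protocol Section 3, repeated in SAP Section 1.1, labels the key secondary FSG endpoint as a central laboratory measure.

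On Visit 99, Protocol Section 4.1 says: "Visit 99 is only applicable to participants who discontinue the study treatment prematurely before Week 40 and decline to complete the remaining study visits", provided they are willing to return at Week 40. The procedures include "measurement of HbA1c, FSG and weight", and the section adds: "This visit is critical to ensure complete data collection for the primary and key secondary endpoints". Footnote b to the Schedule of Activities (Section 1.3) gives the same purpose.

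SAP Section 3 puts all Period II data into the full analysis set regardless of adherence or rescue. SAP Section 4.8.2 imputes missing Week 40 HbA1c from retrieved dropouts in the same arm, with a placebo-based method as the fallback.

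**The concern.** The exception in Section 10.8 evidently exists to keep the two ends of the change score, baseline and Week 40, on one assay. Visit 99 is the other route by which a Week 40 value is obtained, and it has been left off. A site that follows the appendix to the letter could therefore send a Visit 99 HbA1c or FSG sample to a local laboratory without breaching the protocol.

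That value would be compared with a central baseline, or it would have to be discarded as off-definition. Neither document says which. If the question first comes up after unblinding, a choice about primary-endpoint data would be made with treatment assignment known.

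The same HbA1c value is also cut at 7.0, 6.5 and 5.7% for three key secondary endpoints, so an assay offset could change a participant's responder status.

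**Working it through.** The plan gives no figure to reproduce here: the rates of rescue and early stopping in the sample-size section are redacted. The main check is a comparison of the texts, followed by an illustration on assumed inputs.

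**Text comparison**

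1. *Which Week 40 visits are protected?* Section 10.8 names Visit 11 only. The visit-window table in the same appendix groups Visit 11 and Visit 99 in one row with one tolerance. The appendix treats them as alternatives for timing but not for laboratory source.
2. *Who reaches Week 40 through Visit 99?* Under Protocol Section 7.1, a participant who stops study drug "will remain in the study and follow procedures for all remaining study visits", so the default Week 40 visit is Visit 11. Under Section 6.9.1.1, rescued participants also continue through all visits. Visit 99 is left for those who stop, decline the remaining visits and still return.
3. *Does a local Visit 99 value meet the endpoint definitions?* No. Section 8.1 requires central HbA1c, and Section 3 labels FSG as central.
4. *Does the SAP resolve the conflict?* SAP Sections 3, 4.8.1, 4.8.2, 4.9.1.1 and 4.9.1.2 contain no rule on laboratory source. Section 4.8.1 admits unscheduled HbA1c for the primary endpoint visit but does not mention where it was assayed.
5. *Which analyses are exposed?* The treatment-regimen analyses. Visit 99 results come after treatment has stopped, so the efficacy analysis set excludes them.

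**Illustration of size**

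Inputs:
- arm size n = 50 (Protocol Section 9.5)
- one local Visit 99 value in the arm (assumed)
- local-minus-central offset b = 0.2 to 0.3 HbA1c percentage points (assumed)
- retrieval rate ρ = 50 to 70%, the share of participants who stopped or were rescued that have a Week 40 value (assumed)

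With r donors and m missing values in the arm, m/r = (1 − ρ)/ρ, which is 0.30/0.70 = 0.43 at 70% and 1.0 at 50%.

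The local value adds b/n to the arm mean directly. It also moves the donor mean by b/r, and so, on average, each of the m imputed values. Hence

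shift = (b + m·b/r)/n = b(1 + m/r)/n.

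- Low end: 0.2 × 1.43/50 = 0.006 points.
- High end: 0.3 × 2.0/50 = 0.012 points.

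Without the imputation term the shift is 0.2/50 = 0.004 to 0.3/50 = 0.006.

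A wider range takes k = 1 to 5 local values in one arm, offsets of 0.1 to 0.5, and r = m = 5:

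- (1 × 0.1 + 5 × 0.1/5)/50 = 0.004
- (5 × 0.5 + 5 × 2.5/5)/50 = 0.10

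The upper figure needs every one of the five donors to be a local Visit 99 value that is half a point off. These formulas treat imputation as a shift of the donor mean; a regression-based imputation would weight the donor differently. If Visit 99 is added to the protected list and the rule is followed, there are no local Visit 99 values and the shift from this source is zero.

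**The case against.** The strongest reply is that several conditions must coincide: a declared exceptional circumstance, written sponsor approval, a participant who attends Visit 99, and a local sample with no central one. Section 8.1 already demands a central HbA1c. Protocol Section 10.2 (Appendix 2) advises taking a central sample alongside any local one. Section 10.8 widens the Visit 99 window to favour on-site attendance and requires affected participants and activities to be documented, so cases would be traceable.

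Most of this stands, and it limits how often the problem can arise. It does not close the gap. Section 10.8 permits substitution rather than duplication and does not refer to Appendix 2. If the paired-sample advice were enough, the exception for Visits 3 and 11 would be unnecessary. Documentation identifies an affected value but does not say how to analyse it.

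A reader might go further and infer that Visit 99 attendees are the retrieved dropouts, so that one local value would dominate the imputation for its arm. The documents do not support that:

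- Retrieved dropouts in SAP Section 4.8.2 also include rescued participants and early stoppers who stay on schedule, and both groups have the protected Visit 11.
- Where an arm has too few donors for a reliable model, which is when one donor would weigh most, the SAP moves to placebo-based imputation. It sets no threshold for that switch.
- The stopping and retrieval rates needed to size a donor pool are not available in the documents.

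**Conclusion.** The point holds as a minor inconsistency with a specific remedy. Section 10.8 permits a Week 40 HbA1c or FSG value that does not meet the endpoint definitions in Sections 3 and 8.1, and the SAP does not say what happens to it.

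The effect on the primary HbA1c comparison is likely small: about 0.006 to 0.012 points in one arm mean for a single local value, on the assumptions above and only if donor-based imputation is used. The documents give neither a local-to-central offset nor a count of Visit 99 attendees, so these figures are illustrative. The effect on FSG cannot be sized, because no offset is given for it either. Nothing here suggests that the primary conclusion is at risk. The case for acting is that the rule contradicts the endpoint definitions and leaves open a choice about primary-endpoint data.

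**What to change.** 1. In Protocol Section 10.8, extend the retained-central list so that it covers HbA1c and FSG at Visit 3, Visit 11 and Visit 99. This matches the grouping of Visits 11 and 99 in that appendix's window table.
2. In the SAP, before unblinding, state how any local Week 40 HbA1c or FSG value is handled: whether it is analysed or set to missing and imputed, and whether it may serve as a retrieved-dropout donor. This is needed even after the first change, because a local value could still arise in error.

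The cost is a short protocol amendment, with the ethics approval described in Section 10.1.1 and health-authority approval if the amendment is classed as substantial, plus one or two sentences in the SAP. The sponsor already accepts the same restriction at Visit 11. Until the amendment is in place, the restriction could be written into the sponsor's approval whenever the appendix is invoked, since Section 10.8 already requires that approval in writing and provides for added guidance.

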10.9. Appendix 9: Abbreviations and Definitions

| Term | Definition |
|-------------------------|---|
| AE | adverse event |
| ALP | alkaline phosphatase |
| ALT | alanine aminotransferase |
| ANCOVA | analysis of covariance |
| AST | aspartate aminotransferase |
| BG | blood glucose |
| blinding/masking | A double-blind study is one in which neither the participant nor any of the investigator or sponsor staff who are involved in the treatment or clinical evaluation of the subjects are aware of the treatment received. |
| BMI | body mass index |
| CFR | Code of Federal Regulations |
| CHF | congestive heart failure |
| CK | creatinine kinase |
| COA | clinical outcome assessment |
| complaint | A complaint is any written, electronic, or oral communication that alleges deficiencies related to the identity, quality, purity, durability, reliability, safety or effectiveness, or performance of a drug or drug delivery system. |
| CONSORT | Consolidated Standards of Reporting Trials |
| CRF | case report form: a printed, optical, or electronic document designed to record all of the protocol-required information to be reported to the sponsor for each trial participant. |
| CRP | clinical research physician: Individual responsible for the medical conduct of the study. Responsibilities of the CRP may be performed by a physician, clinical research scientist, global safety physician or other medical officer |
| CSR | clinical study report |
| CT | computed tomography |
| D. Bil | direct bilirubin |
| EAS | efficacy analysis set |
| ECG | electrocardiogram |

| | |
|--------------------------------|--|
| EDC | electronic data capture |
| enroll | The act of assigning a participant to a treatment. Participants who are enrolled in the study are those who have been assigned to a treatment. |
| enter | Participants entered into a study are those who sign the informed consent form directly or through their legally acceptable representatives. |
| EQ-5D-5L | European Quality of Life-Dimensions |
| ET | early termination |
| FAS | full analysis set |
| FBG | fasting blood glucose |
| FSG | fasting serum glucose |
| GCP | Good Clinical Practice |
| GGT | gamma-glutamyltransferase |
| GIP | glucose dependent insulinotropic polypeptide |
| GLP-1 | glucagon like peptide-1 |
| GPIU | I8F-MC-GPIU |
| HbA1c | hemoglobin A1c |
| IB | Investigator's Brochure |
| ICF | informed consent form |
| ICH | International Council for Harmonisation |
| IDF | International Diabetes Federation |
| IEC | Independent Ethics Committees |
| investigational product | A pharmaceutical form of an active ingredient or placebo being tested or used as a reference in a clinical trial, including products already on the market when used or assembled (formulated or packaged) in a way different from the authorized form, or marketed products used for an unauthorized indication, or marketed products used to gain further information about the authorized form. See also "IMP." |
| IRB | Institutional Review Boards |
| ISR | injection site reaction |
| IWQOL-Lite-CT | Impact of Weight on Quality of Life-Lite Clinical Trials Version |
| IWRS | Interactive Web Response System |

| | |
|-------------------------|---|
| MedDRA | Medical Dictionary for Regulatory Activities |
| medication error | Errors in the prescribing, dispensing, or administration of a study intervention, regardless of whether or not the medication is administered to the participant or the error leads to an AE. Medication error generally involve a failure to uphold one or more of the five “rights” of medication use: the right participant, the right drug, the right dose, right route, at the right time. In addition to the core five rights, the following may also represent medication errors: |
| | 
 • dose omission associated with an AE or a product complaint • dispensing or use of expired medication • use of medication past the recommended in-use date • dispensing or use of an improperly stored medication • use of an adulterated dosage form or administration technique inconsistent with the medication's labeling (for example, Summary of Product Characteristics, IB, local label, protocol), or • shared use of cartridges, prefilled pens, or both. |
| MEN2 | multiple endocrine neoplasia syndrome type 2 |
| misuse | Use of a study intervention for self-treatment that either is inconsistent with the prescribed dosing regimen, indication, or both, or is obtained without a prescription |
| mITT | modified intention to treat |
| MMRM | mixed model for repeated measures |
| MRI | magnetic resonance imaging |
| MTC | medullary thyroid carcinoma |
| OTC | over-the-counter |
| participant | Equivalent to CDISC term “subject”: an individual who participates in a clinical trial, either as recipient of an investigational medicinal product or as a control |
| PRO | patient-reported outcome |
| QTL | quality tolerance limit |
| QW | once weekly |
| SAE | serious adverse event |
